4.4 TREATMENT BEYOND DISEASE PROGRESSION

Accumulating evidence indicates that a minority of patients treated with immunotherapy may derive clinical benefit from continued treatment despite initial evidence of disease progression (Wolchok et al, 2009). Therefore, participants receiving nivolumab with or without ipilimumab in this study will be permitted to continue study intervention beyond initial Investigator-assessed disease progression (according to Response Evaluation Criteria in Solid Tumors version 1.1 [RECIST v1.1]) if they meet the 2 criteria listed below:

- Investigator-assessed clinical benefit, and
- Participant is tolerating study intervention

The assessment of clinical benefit should take into account whether the participant is clinically deteriorating and unlikely to receive further benefit from continued treatment.

All decisions to continue treatment beyond initial progression must be discussed with the Sponsor and documented in the study records.

Participants should discontinue study intervention upon evidence of further progression, defined as an additional $\geq 10\%$ increase in tumor burden from the time of initial progression (including all target lesions and new measurable lesions).

New lesions are considered measurable at the time of initial progression if the diameters are ≥ 10 mm (except for pathological lymph nodes, which must have a short axis of ≥ 15 mm). Any new lesion considered non-measurable at the time of initial progression may become measurable and therefore included in the tumor burden measurement if the diameter increases to ≥ 10 mm (except for pathological lymph nodes, which must have an increase in short axis to ≥ 15 mm).

For statistical analyses that include the Investigator-assessed progression date, participants who continue treatment beyond initial Investigator-assessed disease progression (according to RECIST v1.1) will be considered to have Investigator-assessed PD at the time of the initial progression event.

4.5 END OF STUDY DEFINITION

A participant is considered to have completed the study if he/she has completed all phases of the study, including the last visit or the last scheduled procedure required for statistical analysis or safety follow-up.

The end of this study is defined as the date when the last visit of the last participant occurs or the date at which the last data point required for statistical analysis or safety follow-up is received from the last participant, whichever occurs later.

The total length of the study, from screening of the first participant to the end of the study, is expected to be approximately 4 years.

5 STUDY POPULATION

Prospective requests for approval of protocol deviations to recruitment and enrollment criteria, also known as waivers or exemptions, are not allowed.

5.1 INCLUSION CRITERIA

Participants are eligible to be included in the study only if all the following criteria apply:

General Inclusion Criteria

1. Participant must be ≥ 18 years of age inclusive, at the time of signing the informed consent.
2. Male or female participants of child-producing potential must agree to use contraception (as detailed in [Appendix 6](#)) or avoidance of pregnancy measures during the study and for 7 and 5 months, respectively, after the last dose.
3. Females of childbearing potential must have a negative serum or urine pregnancy test.

Cancer-specific Inclusion Criteria

4. Histologically or cytologically confirmed cancer that is metastatic, unresectable, or recurrent. Under Amendment 2 only, enrollment will be limited to tumor types known to be responsive to immunotherapy, have high prevalence (> 20%) of CD8 > 15% tumors, and/or have been observed in the study to have tumors transition from CD8 low to CD8 high following initiation of immunotherapy.
 - a. Participants with these tumor types will be eligible to participate regardless of screening CD8 results (either $\geq 15\%$ or $< 15\%$).
 - b. Tumor types for investigation under Amendment 2:
 - i. Melanoma, Gastric, Small cell lung cancer, NSCLC, HCC, Cutaneous squamous cell carcinoma, RCC, Cervical, Gastroesophageal junction cancer, Urothelial bladder cancer, Sarcoma (soft tissue only), Neuroendocrine, SCCHN, Ovarian, Gynecologic malignancies, Merkel Cell, Prostate, Microsatellite instability high Colorectal, Anal (squamous cell only)
5. Participants who have received prior immunotherapy, including prior anti-PD-1 or anti-PD-L1 therapies, will be allowed to participate in this study.
 - a. Participants who received prior anti-PD-1 or anti-PD-L1 may participate only if their prior anti-PD-1 or anti-PD-L1 monotherapy or combination therapy were NOT the last treatment prior to participation on this study.
 - b. Participants who had prior immunotherapies and experienced Grade 1-2 immune-related adverse event (irAE) must have documentation that their irAEs are \leq Grade 1 or baseline using current Common Terminology Criteria for Adverse Events v5.0 (CTCAE v5.0) **and** participants must be off steroid therapy and/or other immunosuppressive therapy, as treatment for irAEs, for ≥ 14 days from Cycle 1, Day 1.
 - c. Participants who experienced Grade 3 irAEs consisting of laboratory abnormalities that were asymptomatic and have now resolved to \leq Grade 1 or baseline **and** participants who have been off steroid and/or other immunosuppressive therapy, as treatment for irAEs, for ≥ 30 days from Cycle 1, Day 1.
6. Concurrent malignancies are permitted if any one of the following applies:
 - a. Previously treated malignancy for which all treatment of that malignancy was completed at least 2 years before enrollment and no evidence of disease exists, or
 - b. With agreement from the Sponsor and Principal Investigator (PI), participants who have a concurrent malignancy that is clinically stable and does not require tumor-directed treatment are eligible to participate if the risk of the prior malignancy interfering with either safety or efficacy endpoints is very low, or
 - c. With agreement from the Sponsor and PI, other malignancies may be permitted if the risk of the prior malignancy interfering with either safety or efficacy endpoints is very low.

7. Provide newly obtained core needle or incisional biopsy of a non-bone tumor lesion not previously irradiated. Fine needle aspiration is not acceptable.
 - a. Biopsies should be obtained from sites that do not pose significant risk to the participant based on the tumor site and the procedure used. Biopsy sites/procedures including, but not limited to, the brain, open lung/mediastinum, pancreas, or endoscopic procedures extending beyond the esophagus, stomach, or bowel would be considered to pose a significant risk to the participant. Procedures to areas that are deemed by the Investigator to be of non-significant risk based on individual clinical scenarios will be permitted.
8. Measurable disease as defined by RECIST v1.1.
 - a. With the exception of prostate cancer participants enrolled under Amendment 3+ who must have measurable disease, participants who do not have measurable disease by RECIST criteria but whose disease can be objectively measured through tumor markers or another disease-specific standard are considered eligible.
9. Eastern Cooperative Oncology Group (ECOG) performance status of 0 or 1.
10. Aspartate aminotransferase (AST) and alanine aminotransferase (ALT) ≤ 3 x upper limit of normal (ULN).
 - a. Participants with hepatocellular carcinoma (HCC) may be eligible provided they have AST and ALT that are ≤ 5.0 x ULN.
11. Hemoglobin ≥ 9 g/dL.
12. Total bilirubin $\leq 1.5 \times$ ULN.
 - a. Participants with HCC are eligible provided they have total bilirubin < 3.0 x ULN and are considered Child-Pugh Class A or Child-Pugh Class B7 (Child-Pugh Class B with a total Child-Pugh score not to exceed 7).
 - b. Participants with Gilbert syndrome must have ≤ 3 x ULN.
13. Creatinine clearance should be ≥ 30 mL/min as estimated by the Cockcroft-Gault equation or other appropriate calculation.
14. Absolute neutrophil count $\geq 1.0 \times 10^9$ /L.
15. Platelets count $\geq 75 \times 10^9$ /L.

Informed Consent

16. Participants must be capable of giving signed informed consent as described in [Appendix 1](#), which includes compliance with the requirements and restrictions listed in the informed consent form (ICF) and in this protocol.

Advanced Prostate Cancer Specific Inclusion Criteria (Amendment 3+)

17. Evidence of stage IV prostate cancer (as defined by American Joint Committee of Cancer criteria) on previous bone, CT and/or MRI scan.

18. Ongoing androgen deprivation therapy (ADT) with a gonadotropin-releasing hormone (GnRH) analogue or a surgical/medical castration with testosterone level of ≤ 1.73 nmol/L (< 50 ng/dL).
19. Participants with skeletal system symptoms who are already on medications (eg, bisphosphonates and/or RANK ligand inhibitors) to strengthen bones are allowed if they were started > 28 days before the first dose of study treatment.
20. Participants must have measurable disease per RECIST v 1.1.
21. Have received and progressed on prior secondary androgen receptor signaling inhibitor therapy (eg, abiraterone, enzalutamide, apalutamide). Progression is defined by one or more of the following 3 criteria:
 - a. Prostate-specific antigen (PSA) ≥ 1.0 ng/mL and rising PSA by at least 2 consecutive measurements a minimum of 1-week apart.
 - b. Soft tissue progression as defined RECIST v 1.1 (Eisenhauer et al., 2009).
 - c. Bone disease progression as defined by 2 new bone lesions (as per Prostate Cancer Clinical Trials Working Group 3 [PCWG3; Scher et al., 2016]).

5.2 EXCLUSION CRITERIA

Participants are excluded from the study if any of the following criteria apply:

General Exclusion Criteria

1. Participants who had a medical condition that required a surgical procedure and were subject to general anesthesia within 4 weeks prior to beginning protocol therapy are excluded except the use of general anesthesia during biopsy procedures, indicated for patient comfort and or safety will be permitted.
2. Pregnant or breastfeeding.
3. Significant gastrointestinal disorder(s) (eg, active Crohn's disease or ulcerative colitis or a history of extensive gastric resection and/or small intestinal resection).
4. Has interstitial lung disease or active, noninfectious pneumonitis.
5. Has a transplanted organ or has undergone allogeneic bone marrow transplant.
6. Has received a live vaccine within 30 days prior to first dose.
7. Known hypersensitivity to a component of protocol therapy.
 - a. Participants with known hypersensitivity to ipilimumab and/or nivolumab are excluded.
8. Uncontrolled concurrent illness including, but not limited to, ongoing or active infection, clinically significant non-healing or healing wounds, symptomatic congestive heart failure, unstable angina pectoris, cardiac arrhythmia, significant pulmonary disease (shortness of breath at rest or on mild exertion), uncontrolled infection, or psychiatric

illness/social situations that, in the opinion of the investigator, would pose a safety concern or limit compliance with study requirements.

Cancer-specific Exclusion Criteria

9. Participants who experienced any \geq Grade 3 symptomatic irAE on a prior immunotherapy study will be excluded from this study regardless of resolution of the irAE.
10. Any known, untreated, brain metastases. Treated participants must be stable 4 weeks after completion of treatment for brain metastases, and image-documented stability is required. Participants must have no clinical symptoms from brain metastases and have not required systemic corticosteroids > 10 mg/day prednisone or equivalent for ≥ 2 weeks prior to first dose of study intervention.
11. Participants with an active, known or suspected autoimmune disease. Participants with type I diabetes mellitus, hypothyroidism only requiring hormone replacement, skin disorders (such as vitiligo, psoriasis, or alopecia) not requiring systemic treatment, or conditions not expected to recur in the absence of an external trigger are permitted to enroll.
12. Participants with a condition requiring systemic treatment with either corticosteroids (> 10 mg daily prednisone equivalent) or other immunosuppressive medications within 14 days of start of study treatment. Inhaled or topical steroids, and adrenal replacement steroid doses > 10 mg daily prednisone equivalent, are permitted in the absence of active autoimmune disease.

Treatment-specific Exclusion Criteria

13. Anticancer chemotherapy, radiotherapy, immunotherapy, or investigational agents within 14 days of first dose of study intervention, provided that all treatment-related AEs have resolved.
 - a. Recent or concurrent non-therapeutic investigational agents that are not anticipated to interfere with study intervention, may be permitted with written agreement from the Medical Monitor. As an exception to this requirement, administration of ^{89}Zr -Df-LAB22M2C in the context of a PICI-sponsored clinical trial does not require written agreement from the Medical Monitor.

5.3 LIFESTYLE CONSIDERATIONS

No restrictions are required.

5.4 SCREEN FAILURES

Screen failures are defined as participants who consent to participate in the clinical study but are not subsequently entered in the study. A minimal set of screen failure information is required to ensure transparent reporting of screen failure participants to meet the Consolidated Standards of Reporting Trials (CONSORT) publishing requirements and to respond to queries from regulatory

authorities. Minimal information includes demography, screen failure details, eligibility criteria, and any serious adverse event (SAE).

Individuals who do not meet the criteria for participation in this study (screen failure) may be rescreened.

6 STUDY INTERVENTION

Study intervention is defined as any investigational intervention(s), marketed product(s), or placebo intended to be administered to a study participant according to the study protocol.

6.1 STUDY INTERVENTION(S) ADMINISTERED

The study interventions to be administered in this study are summarized in [Table 6](#).

Table 6: Study Intervention

Study Intervention Name	Dosage Formulation	Unit Dose Strength(s)	Dosage Level(s)	Route of Administration	Sourcing
Advanced Metastatic Cancer					
Nivolumab	Aqueous solution	10 mg/mL	360 mg (administered with ipilimumab) 480 mg (maintenance)	Intravenous	Bristol-Myers Squibb
Ipilimumab	Aqueous solution	5 mg/mL	1 mg/kg (administered with nivolumab)	Intravenous	Bristol-Myers Squibb
Advanced Prostate Cancer					
Nivolumab	Aqueous solution	10 mg/mL	1 mg/kg (administered with ipilimumab) 480 mg (maintenance)	Intravenous	Bristol-Myers Squibb
Ipilimumab	Aqueous solution	5 mg/mL	3 or 5 mg/kg (administered with nivolumab)	Intravenous	Bristol-Myers Squibb

Participants with $\geq 15\%$ CD8 cells in their tumor biopsy enrolled on the CD8 high arm will be treated with single-agent nivolumab until disease progression. Additionally, participants enrolled on the CD8 high arm in this study could, at disease progression, cross-over to the CD8 low arm; participants with advanced prostate cancer enrolled under Amendment 3+ who cross-over to the CD8 low arm will be placed in Prostate Cohort A.

Nivolumab monotherapy and nivolumab in combination with ipilimumab will be administered as described below.

- *Nivolumab monotherapy (Advanced Metastatic Cancer and Advanced Prostate Cancer):* Nivolumab will be administered at 360 mg as an IV infusion over approximately 30 minutes Q3W \pm 3 days (see [Section 4.3.1](#)). Participants who

continue to show clinical benefit after the first disease assessment will receive nivolumab maintenance 480 mg IV Q4W \pm 3 days until PD or intolerable toxicity (starting at Cycle 5).

- ***Nivolumab in combination with ipilimumab (Advanced Metastatic Cancer):***
Nivolumab will be administered at 360 mg as an IV infusion over approximately 30 minutes Q3W \pm 3 days (see [Section 4.3.2](#)), followed approximately 30 minutes later by ipilimumab, which will be administered at 1 mg/kg as an IV infusion over approximately 30 minutes ([Momtaz et al, 2015](#)). Ipilimumab will be administered Q3W \pm 3 days for the first 2 doses and then every 6 weeks for the 3rd and 4th doses, followed by nivolumab maintenance 480 mg IV Q4W \pm 3 days until PD or intolerable toxicity (starting at Cycle 7). Each of the subsequent doses will be administered as nivolumab maintenance 480 mg IV Q4W \pm 3 days over approximately 30 minutes.
- ***Nivolumab in combination with ipilimumab (Advanced Prostate Cancer):***
Participants in the < 15% CD8 cells (CD8 low) arm will receive either one of the following combinations of nivolumab and ipilimumab:
 - **Prostate Cohort A:** Nivolumab will be administered at 1 mg/kg as an IV infusion over approximately 30 minutes Q3W (see [Section 4.3.2](#)), followed approximately 30 minutes later by ipilimumab, which will be administered at 3 mg/kg as an IV infusion over approximately 30 minutes ([Momtaz et al, 2015](#)) Q6W for two 6 week cycles. After completion of 2 cycles, nivolumab maintenance 480 mg IV Q4W \pm 3 days will be administered until PD or intolerable toxicity.
 - **Prostate Cohort B:** Nivolumab will be administered at 1 mg/kg as an IV infusion over approximately 30 minutes Q3W (see [Section 4.3.2](#)), followed approximately 30 minutes later by ipilimumab, which will be administered at 5 mg/kg as an IV infusion over approximately 30 minutes ([Momtaz et al, 2015](#)) Q6W for two 6 week cycles. After completion of 2 cycles, nivolumab maintenance 480 mg IV Q4W \pm 3 days will be administered until PD or intolerable toxicity.

For all study interventions, either a peripheral IV or central port or line is acceptable for infusion. Administration of study intervention will be performed in a monitored setting in which there is immediate access to trained personnel and adequate equipment and medicine to manage potentially serious reactions.

6.2 PREPARATION/HANDLING/STORAGE/ACCOUNTABILITY

Participant weight will be assessed at Screening and Day 1 of each cycle. Dose preparations are based on the participant's weight and should be adjusted if the participant has a 10% change in comparison to their initial weight on Cycle 1, Day 1.

The Investigator or designee must confirm that appropriate temperature conditions have been maintained during transit for all study intervention received and any discrepancies are reported and resolved before use of the study intervention.

Only participants enrolled in the study may receive study intervention, and only authorized site staff may supply or administer study intervention. All study intervention must be stored in a secure, environmentally controlled, and monitored (manual or automated) area in accordance with the labeled storage conditions with access limited to the Investigator and authorized site staff.

The Investigator, institution, or the head of the medical institution (where applicable) is responsible for study intervention accountability, reconciliation, and record maintenance (ie, receipt, reconciliation, and final disposition records).

Further guidance and information for the final disposition of unused study interventions are provided in the Pharmacy Manuals.

6.3 MEASURES TO MINIMIZE BIAS: RANDOMIZATION AND BLINDING

6.3.1 Intervention Assignment

The advanced metastatic cancer portion of this study is not randomized. Treatment assignment will be based on the percentage of tumoral CD8 cells at the initial biopsy. Participants who have a tumor with $\geq 15\%$ CD8 cells will receive nivolumab monotherapy, and participants who have a tumor with $< 15\%$ CD8 cells will receive ipilimumab in combination with nivolumab.

The first 10 advanced prostate cancer participants who enroll with a tumor with $< 15\%$ CD8 cells will be randomly allocated to receive nivolumab 1 mg/kg in combination with ipilimumab 3 mg/kg (Prostate Cohort A) or nivolumab 1 mg/kg in combination with ipilimumab 5 mg/kg (Prostate Cohort B) in a 1:1 ratio.

The remaining 10 advanced prostate cancer participants will not be randomly allocated but instead assigned to an intervention cohort based on the safety observed in both cohorts. If Prostate Cohort B is determined to have a tolerable safety profile (per [Section 6.6.1.4](#)), the remaining 10 advanced prostate cancer participants will be assigned to Prostate Cohort B. If the safety profile of Prostate Cohort B is deemed unacceptable, the remaining 10 advanced prostate cancer participants will be assigned to Prostate Cohort A.

All advanced prostate cancer participants who have a tumor with $\geq 15\%$ CD8 cells will receive nivolumab monotherapy. Participants who are randomly allocated but do not receive study intervention for any reason may be replaced. Randomization will be performed by the Sponsor.

Study intervention will be administered by site personnel and tracked using drug accountability records.

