6.6.1.4 Additional Safety Precautions (Advanced Prostate Cancer Cohort Only)

The safety profile for nivolumab (1 mg/kg) in combination with ipilimumab (3 mg/kg) is well established in melanoma and HCC at more frequent ipilimumab administration (Q3W vs Q6W) than proposed for this cohort ([Opdivo USPI, 2020](#)). Hence, concurrent enrollment will be pursued with participants allocated to regimens containing either ipilimumab 3 mg/kg or 5 mg/kg Q6W for up to 2 doses in combination with nivolumab 1 mg/kg. As the combination regimen with ipilimumab 5 mg/kg has not been extensively studied, in addition to adverse events being reviewed by the Sponsor on an ongoing basis and investigator meetings convening approximately every 2 weeks to discuss and review safety events, a safety pause is included.

Enrollment will pause until all participants have been followed for at least 6 weeks. During the pause, new participants may be consented and screened, but not initiated on study intervention. The safety pause will apply to both cohorts to preserve random allocation; however, the safety assessment as follows will apply to the ipilimumab 5 mg/kg cohort specifically. The initial 5 participants enrolled in the ipilimumab 5 mg/kg cohort will be observed for the occurrence of treatment-related adverse events (TRAEs) necessitating discontinuation of both agents (AEs requiring discontinuation are included in [Table 9](#)) from the beginning of treatment through completion of the first cycle (ie, 6 weeks).

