If 3 or fewer of the first 5 participants in the ipilimumab 5 mg/kg cohort (Prostate Cohort B) experience a TRAE leading to discontinuation of both agents, an additional 10 participants will be enrolled to receive nivolumab 1 mg/kg Q3W and ipilimumab 5 mg/kg Q6W for 2 cycles, then nivolumab maintenance 480 mg Q4W until PD or intolerable toxicity (Prostate Cohort B). If 4 or more of the first 5 participants of the ipilimumab 5 mg/kg cohort (Prostate Cohort B) experience a TRAE leading to discontinuation of both agents, an additional 10 participants will be enrolled to receive nivolumab 1 mg/kg Q3W and ipilimumab 3 mg/kg Q6W for 2 cycles, then nivolumab maintenance 480 mg Q4W until PD or intolerable toxicity (Prostate Cohort A). Only TRAEs leading to treatment discontinuation of both agents occurring up until the 5th participant in each cohort completes Cycle 1 will be included—dose delays for adverse events not otherwise meeting criteria at that time will not be counted. The stopping rule was chosen as this

corresponds to a > 80% chance that the toxicity rate in the cohort is > 40%, assuming a beta (0.8, 1.2) prior.

If either prostate cohort demonstrates 8 or greater TRAEs requiring discontinuation of therapy at any time, enrollment will be suspended until an ad hoc safety review convenes and provides a recommendation, as described above.

Table 9: Toxicity Criteria Requiring Permanent Treatment Discontinuation of Both Nivolumab and Ipilimumab (Amendment 3+ Advanced Prostate Cohort Only)

Participants should be monitored for the occurrence of any of the following AEs that are considered by the Investigator to be possibly, probably, or definitely related to ipilimumab, nivolumab, or the immunotherapy combination.
 
Treatment with all study intervention should be monitored for the occurrence of any of the following TRAEs, and if any of these events occur, action should be taken as follows:

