50	10	5	(3.7, 19.9)
40	10	4	(3.2, 21.2)
30	10	3	(2.6, 23.2)
160	20	32	(14.2, 26.5)
125	20	25	(13.5, 27.4)
100	20	20	(12.9, 28.3)
75	20	15	(11.9, 29.6)
50	20	10	(10.4, 31.8)
40	20	8	(9.5, 33.2)
30	20	6	(8.3, 35.2)
160	30	48	(23.1, 37.1)
125	30	38	(22.6, 38.5)
100	30	30	(21.4, 39.0)
75	30	22	(19.6, 39.6)
50	30	15	(18.1, 42.6)
40	30	12	(16.9, 44.0)
30	30	9	(15.2, 46.0)

A total of approximately 20 advanced prostate cancer participants with CD8 low tumors will be treated with the combination of nivolumab and ipilimumab, in 1 of 2 dosing cohorts. The first 10 participants enrolled will be randomly allocated by the Sponsor into one of two cohorts (5 participants per cohort) to evaluate the safety of different dose levels of ipilimumab in combination with nivolumab. If the higher dose level (ipilimumab 5 mg/kg + nivolumab 1 mg/kg) is determined to be tolerable per [Section 6.6.1.4](#), an additional 10 participants will be enrolled at this higher dose level (Prostate Cohort B). If the safety profile of Prostate Cohort B is deemed unacceptable, an additional 10 participants will be enrolled at the lower dose level (Prostate Cohort A).

We hypothesize that higher doses of ipilimumab will demonstrate a larger proportion of participants who convert from CD8 low to CD8 high. There is no prior for the expected proportion of participants who will convert from CD8 low to CD8 high at the various dose levels of ipilimumab. With 15 participants enrolled in Prostate Cohort B, Table 12 provides 95% credible intervals for possible CD8 conversion rates in the cohort. For example, a 95% credible interval assuming 6/15 (40%) participants converting in the cohort would be (17.7%, 64.9%).

Table 12: Credible Intervals for CD8 Conversion

Subgroup Size	CD8 Conversion Rate	Expected Successes	95% Credible Interval
15	20	3	(4.7, 42.8)
15	40	6	(17.7, 64.9)
15	60	9	(35.1, 82.3)

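### Protocol 6.3.1 bases assignment of the last 10 prostate participants on both cohorts' safety, but the operative rule reads Cohort B only, and SAP 4.4 gives a different consequence at the same trigger

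*Protocol*

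**What the plan says.** The first 10 prostate participants with CD8-low tumors are randomized 1:1, 5 per cohort (Protocol 6.3.1 and 9.1). For the remaining 10, Section 6.3.1 opens by saying they are "assigned to an intervention cohort based on the safety observed in both cohorts". Its next two sentences depend on Cohort B alone and refer to 6.6.1.4. The second reads: "If the safety profile of Prostate Cohort B is deemed unacceptable, the remaining 10 advanced prostate cancer participants will be assigned to Prostate Cohort A".

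Section 6.6.1.4 pauses enrollment in both cohorts but states that "the safety assessment as follows will apply to the ipilimumab 5 mg/kg cohort specifically". With 3 or fewer of 5 affected, 10 more enter Cohort B. The other branch begins "If 4 or more of the first 5 participants of the ipilimumab 5 mg/kg cohort (Prostate Cohort B) experience a TRAE leading to discontinuation"; the discontinuation meant is that of nivolumab and ipilimumab together. The consequence in that branch is that "an additional 10 participants will be enrolled to receive nivolumab 1 mg/kg Q3W and ipilimumab 3 mg/kg Q6W for 2 cycles", which is the Cohort A regimen. The justification is that the limit "corresponds to a > 80% chance that the toxicity rate in the cohort is > 40%, assuming a beta (0.8, 1.2) prior". Section 9.1 and the Synopsis repeat the rule that depends only on Cohort B. Section 6.6.1.4 also suspends enrollment, pending an ad hoc review, if either cohort has 8 or more related events requiring discontinuation.

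SAP 4.4 uses the same 4-of-5 trigger with a different consequence: enrollment into the 5 mg/kg cohort is suspended and an ad hoc review makes a recommendation. It contains no automatic move to Cohort A. SAP 4.1 still randomizes about 20 participants 1:1. SAP Section 6, which lists differences from the protocol, mentions neither point.

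**The concern.** A site, an ethics committee or the sponsor's own team cannot tell from Section 6.3.1 whether Cohort A's first 5 participants bear on the decision. The opening clause says they do, and no operative rule uses them. The gap matters if Cohort B reaches its limit and Cohort A has also shown heavy toxicity. The protocol text then enrolls 10 further participants, half the planned CD8-low prostate sample of 20, on the Cohort A regimen without reference to data already in hand. A reader of the SAP would expect enrollment into the 5 mg/kg cohort to stop and a review to convene. Two current documents therefore describe different events at the same safety trigger.

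**Working it through.** **Inputs.** Prior beta(0.8, 1.2), toxicity limit 40%, probability criterion above 80%, threshold 4 of the first 5 (Protocol 6.6.1.4). Five participants per cohort initially (9.1) and 10 added, so at most 15 in the expanded cohort.

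**1. Reproduce the plan's own figure.** With x events in n participants the posterior is beta(0.8 + x, 1.2 + n − x). For n = 5:

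| Events of 5 | Posterior | Pr(rate > 40%) |
|---|---|---|
| 3 | beta(3.8, 3.2) | 77.6% |
| 4 | beta(4.8, 2.2) | 94.2% |
| 5 | beta(5.8, 1.2) | 99.3% |

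Four is the first count above 80%, so the stated basis reproduces and the threshold itself is not in error.

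**2. Read the same calculation on Cohort A, as illustration only.** At 4/5 or 5/5 in Cohort A the probabilities are the same 94.2% and 99.3%, above the criterion that triggers the switch away from Cohort B. The protocol rule would still send the next 10 participants there.

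**3. Are Cohort A's data available at that moment?** Yes. Both cohorts pause together until all participants have at least 6 weeks of follow-up, and the counting window refers to the fifth participant in each cohort finishing Cycle 1.

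**4. Would the 8-event suspension act first?** Counted by participant, no: 5 is fewer than 8. After 5/5, at least 8 − 5 = 3 of the added 10 would have to be affected; after 4/5, at least 4. The participant reading fits the number: at n = 15, 7 events give 68.1% and 8 give 83.4%, so 8 is the first count above 80%. Counted as events, 5 participants could in principle accumulate 8, but this is a suspension and not part of the assignment rule.

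**5. How often would both cohorts reach 4 of 5?** For a true rate p, P(4 or more of 5) = 5p⁴(1 − p) + p⁵. At p = 0.4 this is 5 × 0.0256 × 0.6 + 0.01024 = 0.0870. The documents give no true 6-week discontinuation rates, so p is assumed, as is independence between cohorts.

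| Rate in each cohort | One cohort reaches 4 of 5 | Both do (squared) |
|---|---|---|
| 30% | 3.1% | 0.1% |
| 40% | 8.7% | 0.8% |
| 50% | 18.8% | 3.5% |
| 60% | 33.7% | 11.4% |
| 70% | 52.8% | 27.9% |

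With a lower rate in Cohort A the joint chance falls: 0.06% for A 20% and B 40%, 0.6% for A 30% and B 50%, 2.9% for A 40% and B 60%, 6.3% for A 50% and B 60%.

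**The case against.** The best defense is that the clause about both cohorts is a loose lead-in. The sentences after it state the rule, and 6.6.1.4, 9.1 and the Synopsis agree with them. That stands in part. A reader might infer that the protocol gives opposite instructions, but no passage sets a Cohort A criterion or a different assignment. The protocol text is inconsistent, not opposed.

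The focus on Cohort B is also explained. Section 6.6.1.4 calls the 3 mg/kg combination well established at more frequent dosing and the 5 mg/kg combination less studied. A reader might infer that this support comes only from melanoma and hepatocellular carcinoma. Section 2.2.3 says otherwise: it cites a trial of the combination in metastatic castration-resistant prostate cancer at nivolumab 1 mg/kg and ipilimumab 3 mg/kg every 3 weeks for up to 4 cycles. A rule based only on Cohort B may be deliberate. In that case the clause in 6.3.1 misstates it.

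A reader might further infer that Cohort A is unprotected whatever it shows. The documents do not support that. Besides the 8-event suspension there is ongoing Sponsor review, an investigator meeting about every 2 weeks, and the Sponsor's right to terminate for adverse-event incidence or severity (10.1.9). These checks carry no threshold. Section 9.3.1 extends monitoring to prostate participants, but the numerical toxicity rule in 9.3.1.1 is worded for the metastatic arms. Table 14 starts at 20 participants, above Cohort A's maximum of 15. There is no independent monitoring committee.

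Finally, the case where both cohorts reach the limit is rare at moderate rates. That is correct, and it limits the practical size of the problem. It does not remove the inconsistency or the conflict with the SAP.

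**Conclusion.** The inconsistency is real and should be corrected. Section 6.3.1 names both cohorts as the basis for assigning the last 10. The operative rule uses Cohort B's first 5 only. SAP 4.4 prescribes suspension and review where the protocol prescribes enrollment into Cohort A, and SAP Section 6 does not list the difference.

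As written in the protocol, a Cohort A with 4/5 or 5/5 affected would still receive 10 participants, at a 94.2% or 99.3% posterior probability of exceeding 40%. The chance of reaching that situation depends on rates the documents do not give. It ranges from about 0.1% to 27.9% for equal rates of 30% to 70%, assuming independent cohorts, and is lower if Cohort A is less toxic than Cohort B. The 40% that the protocol uses elsewhere (9.3.1.1) is a 12-week toxicity rate assumed for standard therapy, so it is only a loose guide to the 6-week rate.

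The protocol is taken to govern assignment, because its clause giving the SAP precedence sits under statistical analyses (9.4). If the SAP were held to govern, the automatic move to Cohort A would not occur, which makes reconciliation more necessary. The 4-of-5 threshold is arithmetically sound and is not criticized here.

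**What to change.** Reconcile the Protocol Synopsis, 6.3.1, 6.6.1.4 and 9.1 with SAP 4.1 and 4.4, so that all of them agree on two points: whether, and if so how, Cohort A's observed safety enters the assignment of the last 10 participants; and what follows when Cohort B reaches 4 of 5. If a difference between protocol and SAP is intended, list it in SAP Section 6. The same revision should state whether the limit of 8 counts participants or events. It should also supply the description of the ad hoc review, which 6.6.1.4 says is given above but which appears only in SAP 4.4. Which rule applies is a clinical decision for the sponsor, and none is proposed here.

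The cost is amendment wording in two documents. No new data are needed and no further pause is required, because both cohorts already pause together and Cohort A's first-cycle data are collected in that window.
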